5.5 Prior and Concomitant Therapy

No additional medications or therapies will be provided during this study beyond omeprazole 40mg once daily or the equivalent which is recommended in all patients undergoing endoscopic resection. All prior or concomitant medical therapies can be continued during this study.

5.6 Packaging and Labeling

The ECM product will arrive in a sterile, airtight sleeve. Each sleeve will be inside of a sealed box.

5.7 Masking/Blinding of Study

Patients will be randomized during the procedure based on our current understanding of risk factors for post-resection scarring and stricture formation. Thus, randomization will be primarily determined by the size of the defect and number of resections performed (during the initial endoscopy).

5.8 Receiving, Storage, Distribution and Return

5.8.1 Receipt of Investigational Devices

The ECM product is already stocked and stored in our lab located in the SMH Alfred Main endoscopy suite. Additional inventory will similarly be shipped directly from the manufacturer. At the initiation of the study, investigators will count and verify current inventory. This will be repeated whenever inventory is expanded.

5.8.2 Storage

The manufacturer instructions recommend storage in a clean, dry environment at a temperature of 15 – 35 C. Our laboratory temperature will be maintained within this range. Storage in our laboratory will also prevent unintended/unauthorized use. The product is sterilized and once opened must be used.

5.8.3 Distribution of Study Device

For patients randomized to receive ECM, the ECM will be prepared in the endoscopy suite for application. This will include notation of the manufacturer, catalog number, batch code, and serial number, in addition to details regarding the procedure (including patient information, procedure date and time). A running total number of devices in inventory will be maintained. Any products inadvertently damaged or not used will be noted. Inventory audits will be performed on a monthly basis.

5.8.4 Return or Destruction of Study Device

We will order clinical supply as needed and dispose of unused supply. We do not anticipate needing to return supplies.

6 Study Procedures

6.1 Visit 1

Patients will be recruited from the Barrett's Esophagus Clinic. Patients referred for endoscopic evaluation of Barrett's esophagus with high grade dysplasia, esophageal nodules or early esophageal cancer and are scheduled for EMR, will be screened using inclusion and exclusion criteria outlined above. Patients meeting inclusion criteria will be consented for study inclusion and will be asked to complete the Mayo Dysphagia Questionnaire.

6.2 Visit 2

Visit 2 refers to the procedure during which the patient will undergo planned EMR of the esophageal lesion. Visits 1&2 may take place on the same date. Patients will undergo endoscopy and those amenable to standard EMR will be randomized to receive ECM or receive standard of care (i.e., observation). ECM will be applied to patients in the manner described above.

6.3 Visit 3

All patients will be scheduled to return in approximately 12-16 weeks (up to 6 months) following EMR for follow-up endoscopic evaluation. Patients will repeat the Mayo Dysphagia Questionnaire prior to endoscopy. During endoscopy, the EMR site will be inspected and multiple pictures will be taken in white-light as well as electron chromoendoscopy (i.e., narrow band imaging). Thereafter, standard submucosal saline injection of the healed EMR site will be performed, and the endoscopist will record whether no lift, a partial lift, or complete lift was observed. Symptomatic structuring will be treated with standard pneumatic dilation.

Schedule of Events			
Study Activity	Baseline*	Procedure*	Follow-up procedure (3-4 months)
Consent	X		
History	X		X
Physical Exam	X	X	X
Disease State Symptom Survey	X		X
Concurrent Medications	X	X	X
Adverse Events		X	X
Serious Adverse Events		X	X

*Baseline and Procedure may be on the same date/visit.

7 Statistical Plan

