3.1 General Design

This is a randomized study on the efficacy of ECM in promoting constructive healing following endoscopic resection (EMR). 20 patients anticipated to undergo endoscopic resection will be recruited in the outpatient setting from the Barrett's Esophagus Unit. Prior to endoscopy, patients will complete a standardized questionnaire (Mayo Dysphagia Questionnaire) and the physician will use the Mellow-Pinkas scale to assess baseline dysphagia. Patients with lesions that lift and are amenable to cap-assisted EMR will be randomized to receive ECM to the defect site vs. standard of care. All patients should be on standard of care double dose proton-pump inhibitor therapy (Omeprazole 40mg PO daily or the equivalent); if this has not been initiated they will be provided a prescription .

In both groups, patients will be brought back for repeat standard of care clinic and endoscopic assessments in 12-16 weeks, or sooner if needed. A clinical dysphagia assessment will be performed with repeat of the above questionnaires. Endoscopy will involve inspection of the wound site, and images in white-light and electron chromoendoscopy will be taken for blinded evaluation later. Submucosal saline injection at the wound site will be performed to determine its ability to lift.

Any patients receiving esophageal dilations will be noted. Patients requiring esophagectomy will be excluded from the primary objective of the study but their surgical specimen at the site of endoscopic resection will be evaluated for evidence of constructive healing.

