4.3 Subject Recruitment, Enrollment and Screening

Subjects will be recruited from the endoscopic practice of the Principal Investigator and Co-Investigator. Patients will undergo screening for inclusion and exclusion criteria at the time of clinical consultation.

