5.2 Method for Assigning Subjects to Treatment Groups

Patients will be randomized using prepackaged envelopes to ECM or standard of care and stratified based on the size and number of EMR performed during the procedure. Thus, randomization will occur during the procedure immediately following resection.

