7.2 Statistical Methods

Descriptive Statistics

Univariate descriptive statistics and frequency distributions will be calculated, as appropriate for all variables. Baseline values for demographic, clinical, and outcome variables (primary and secondary) will be tabulated for the treatment groups. These analyses will help identify potential confounding variables to be used as covariates in sensitivity analyses. Distributions across subgroups used in randomization will be compared to assess whether the randomization was successful in equalizing distributions of these prognostic variables across treatment groups. Putative prognostic variables that will be investigated through these descriptive analyses include variables such as presence of submucosal lift, esophageal caliber, need for esophageal dilation, and score on the Mayo Dysphagia Questionnaire.

Handling of Missing Data

Given the small number of patients and minimal follow-up time we do not anticipate missing data.

Primary Hypothesis: To assess the efficacy of ECM products in promoting constructive healing as determined by the ability of the resection site to lift with saline injection during follow-up.

A student unpaired t-test will be performed to compare the incidence of successful lift in the area of prior EMR among ECM and non-ECM groups.

Secondary Hypothesis: Secondary endpoints include efficacy of ECM in preventing symptomatic esophageal stricture formation requiring dilation, preventing dysphagia as determined by questionnaires, and mitigating formation of post-resection scarring as determined by blinded comparison of pre- and post-resection images (taken using white-light endoscopy and electron chromoendoscopy).

Dysphagia questionnaire: student paired t-test will compare the pre and post treatment scores between both groups.

Esophageal diameter: student paired t-test will compare the pre and post treatment sizes between groups.

Interim Analysis

As this is a small pilot study, we will not perform an interim analysis. Any serious adverse events will prompt immediate reevaluation of study methods.

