8.4 Unblinding Procedures (Breaking the Blind) (as necessary if the study is blinded)

Unblinding will occur for any serious adverse event related to the ECM, or if execution of other therapies such as esophageal surgery, will be impacted by knowledge of the presence of ECM.

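### The primary lift grade is read live by a Visit 3 endoscopist whom no section masks to arm, while blinded reading is reserved for a secondary endpoint

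*Combined protocol and SAP*

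**What the plan says.** **The primary reading.** Section 3.2 makes mucosal lift on fluid injection the primary endpoint. In 6.3 the healed site is inspected and photographed. Only then comes the saline: "Thereafter, standard submucosal saline injection of the healed EMR site will be performed". The response is graded on the spot, in three levels: "the endoscopist will record whether no lift, a partial lift, or complete lift was observed". Section 1.5.2 adds only that the person injecting is experienced.

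**Masking.** Section 5.7 carries the masking heading, but its text is about allocation: "Thus, randomization will be primarily determined by the size of the defect and number of resections performed". Section 8.4 provides for unblinding after a serious event related to the ECM, or if other therapy such as surgery "will be impacted by knowledge of the presence of ECM". It does not say who was blinded.

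**Where blinding is planned.** Section 3.1 says "images in white-light and electron chromoendoscopy will be taken for blinded evaluation later". Sections 3.3 and 7.2 tie this to a secondary endpoint, "mitigating formation of post-resection scarring as determined by blinded comparison of pre- and post-resection images".

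**Who learns the arm.** Under 5.2, "randomization will occur during the procedure immediately following resection", and 5.3 has the sheet fixed to the defect in that same procedure. Section 4.3 states: "Subjects will be recruited from the endoscopic practice of the Principal Investigator and Co-Investigator".

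**How the grade is analysed.** Section 7.1 sizes the trial on a two-level endpoint, lift present or absent. Section 7.2 compares the incidence of *successful* lift between arms with an unpaired t-test. Neither says where a partial lift falls.

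**The concern.** How far a site lifts is a visual judgement with an intermediate category. A grader who knows the arm can, without intent, read borderline lifts more generously in one arm than in the other. The plan protects its secondary scarring endpoint against this and leaves the primary endpoint without the same protection. Because the images are described before the injection, the blinded readers as planned would see nothing from which to judge lift.

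The lift comparison is the trial's efficacy result, and section 1.5.1 offers the data as possible groundwork for larger trials. If the grader knew the arm, a reader could not separate an effect of ECM from a difference in grading.

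**Working it through.** **1. Reproducing the plan's figure.** Inputs from 7.1: 20% against 80% lift, alpha 0.05, power 0.8. Sidedness is not stated; I take two-sided. With the pooled formula and no continuity correction:

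n = [1.960 × √(2 × 0.5 × 0.5) + 0.842 × √(0.2 × 0.8 + 0.8 × 0.2)]² / (0.8 − 0.2)² = (1.386 + 0.476)² / 0.36 = 9.6, so 10 per arm.

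This matches the protocol. Enumerating both binomials at 10 per arm gives power 0.805 for the t-test on 0/1 data. The sample-size arithmetic is not in dispute.

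**2. Differential grading when ECM does nothing.** The documents give no misgrading rate, so the shares below are assumptions. Let p be the true lift rate in both arms (20%, the protocol's control rate, or 50%), and e the share misgraded.

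- Graded ECM rate: p + (1 − p)e.
- Graded control rate: p if only ECM non-lifts are graded up (one direction), or p(1 − e) if control lifts are also graded down (both directions).
- False 'ECM better' rate: the total binomial probability, at 10 per arm, of tables with ECM higher and two-sided p ≤ 0.05. The nominal figure is 2.5%.

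| Misgrading | Graded rates (ECM / control), p = 20% | t-test | Fisher | Graded rates, p = 50% | t-test | Fisher |
|---|---|---|---|---|---|---|
| None | 20% / 20% | 1.5% | 0.4% | 50% / 50% | 2.1% | 0.6% |
| 10%, one direction | 28% / 20% | 4.3% | 1.5% | 55% / 50% | 3.5% | 1.2% |
| 10%, both directions | 28% / 18% | 5.4% | 1.9% | 55% / 45% | 5.6% | 2.0% |
| 20%, one direction | 36% / 20% | 9.4% | 3.9% | 60% / 50% | 5.6% | 2.0% |
| 20%, both directions | 36% / 16% | 13.5% | 5.9% | 60% / 40% | 12.7% | 5.3% |

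In patients, the last row at p = 50% means 10 × 0.5 × 0.2 = 1 regrade in each arm on average. At p = 20% it means 10 × 0.8 × 0.2 = 1.6 in ECM and 10 × 0.2 × 0.2 = 0.4 in control.

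**3. Where partial lift falls.** For the t-test on 0/1 data, t = d / √{[p₁(1 − p₁) + p₂(1 − p₂)] / 9} on 18 degrees of freedom, where d is the difference in proportions. Suppose complete lifts are 8/10 against 2/10: t = 0.6 / √(0.32 / 9) = 3.18, p = 0.005 (Fisher 0.023). Counting partial lifts as lift then gives:

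| Partial lifts added (ECM, control) | Table | t-test p |
|---|---|---|
| 0, 2 | 8/10 v 4/10 | 0.074 |
| 1, 2 | 9/10 v 4/10 | 0.018 |
| 1, 1 | 9/10 v 3/10 | 0.004 |
| 2, 2 | 10/10 v 4/10 | 0.002 |

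Only the lopsided first row loses significance. Equal numbers of partial lifts leave d unchanged, so the t-test conclusion holds except at the edge of the scale. For example, 4/10 v 0/10 gives t = 0.4 / √(0.24 / 9) = 2.45, p = 0.025, while 5/10 v 1/10 gives t = 0.4 / √(0.34 / 9) = 2.06, p = 0.054.

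**The case against.** **Masking may exist in practice.** A reader might infer that the Visit 3 grader is unmasked, or is the person who placed the ECM. The documents establish neither. Section 8.4 presupposes some blind. Section 4.3 does not limit follow-up endoscopy to the index operator, and 8.3.2 mentions participating sub-investigators. Clips are meant to slough (5.3), so a different endoscopist might see no cue. What stands is that no section assigns masking to the lift reading or keeps the index operator from doing it.

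**The bias is assumed.** This is right. At 10% misgrading the t-test rate stays at or below 5.6%, and Fisher's exact test stays within 2.5%. The figures above 10% need 20% in both directions.

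**Small numbers are fragile anyway.** One might cite 7/10 v 2/10 (t-test p = 0.024) against 6/10 v 2/10 (p = 0.074) to show that a single grade decides the trial. That sensitivity comes from having 10 per arm and would remain under perfect masking. It is not evidence of grading bias.

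**Partial lift is nearly defined.** Read plainly, 7.1 counts any lift as present. The doubt rests on one adjective in 7.2, so this is a minor gap.

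**It is a feasibility pilot, and some papers are not supplied.** No confirmatory claim depends on the result, but the protocol does state an efficacy objective and power a test. The CRF is not among the pages supplied and might hold grade criteria. It would not repair 5.7.

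**Conclusion.** The point holds as a gap in specification with a cheap remedy. The plan leaves open who is masked for its primary reading, and its blinded evaluation, as written, cannot cover lift. Differential grading therefore cannot be excluded for the primary result.

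Its size is unknown. With no true effect and the assumed misgrading shares, the planned t-test's false 'ECM better' rate goes from 1.5-2.1% to about 3.5-5.6% at 10% and 5.6-13.5% at 20%, across one or both directions. These ranges rest on 10 per arm, a true lift rate of 20% or 50%, and a two-sided 0.05 test. They show what could happen and do not estimate what will.

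The documents do not support saying that the trial is unmasked or its result biased. Nor do they support treating the undefined place of partial lift as an equal problem: it matters mainly if partial lifts fall unevenly between arms. The sponsor should make the change, but it is not a bar to running the study.

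**What to change.** 1. **Section 6.3:** also capture images or a short recording of the saline injection, and include them in the planned blinded image evaluation, with written criteria for none, partial and complete lift. Use the masked grade for the primary analysis and keep the live grade as a sensitivity analysis. Where staffing already allows, an alternative is live grading by a Visit 3 endoscopist who did not perform the index procedure and is masked to arm.
2. **Sections 5.7 and 8.4:** state in 5.7 who is masked and for which assessments, and make 8.4 agree.
3. **Minor, sections 7.1 and 7.2:** before the first Visit 3, state that partial and complete lift both count as lift, the plain reading of 7.1, and report complete-only as a sensitivity analysis.

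**Cost:** wording in five sections, one short grading scale, and at most 20 recordings to make and read. No patients or visits are added. The plan does not name or count its blinded readers, so the sponsor should confirm who would take on this reading. Recorded views may be less clear than the live view, which is why the live grade is kept. Retained clips or tacks may sometimes reveal the arm.

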7.1 Sample Size Determination

A power analysis was performed for this two independent sample study with a dichotomous endpoint (presence of a saline lift during follow-up EGD). We assume 20% of patients receiving standard of care and no ECM will have a submucosal lift vs. 80% of patients receiving ECM will have submucosal lift. Using a power of 0.8, and alpha of 0.05, this equates to a sample size of 10 for each group for a total of 20 subjects.

7.2 Statistical Methods

Descriptive Statistics

Univariate descriptive statistics and frequency distributions will be calculated, as appropriate for all variables. Baseline values for demographic, clinical, and outcome variables (primary and secondary) will be tabulated for the treatment groups. These analyses will help identify potential confounding variables to be used as covariates in sensitivity analyses. Distributions across subgroups used in randomization will be compared to assess whether the randomization was successful in equalizing distributions of these prognostic variables across treatment groups. Putative prognostic variables that will be investigated through these descriptive analyses include variables such as presence of submucosal lift, esophageal caliber, need for esophageal dilation, and score on the Mayo Dysphagia Questionnaire.

Handling of Missing Data

Given the small number of patients and minimal follow-up time we do not anticipate missing data.

Primary Hypothesis: To assess the efficacy of ECM products in promoting constructive healing as determined by the ability of the resection site to lift with saline injection during follow-up.

A student unpaired t-test will be performed to compare the incidence of successful lift in the area of prior EMR among ECM and non-ECM groups.

Secondary Hypothesis: Secondary endpoints include efficacy of ECM in preventing symptomatic esophageal stricture formation requiring dilation, preventing dysphagia as determined by questionnaires, and mitigating formation of post-resection scarring as determined by blinded comparison of pre- and post-resection images (taken using white-light endoscopy and electron chromoendoscopy).

Dysphagia questionnaire: student paired t-test will compare the pre and post treatment scores between both groups.

Esophageal diameter: student paired t-test will compare the pre and post treatment sizes between groups.

Interim Analysis

As this is a small pilot study, we will not perform an interim analysis. Any serious adverse events will prompt immediate reevaluation of study methods.

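### 7.2 specifies no comparison of lift that uses the factors randomization is stratified by, and leaves sensitivity covariates to be picked after the tables are seen

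*Combined protocol and SAP*

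**What the plan says.** **Allocation.** Section 5.2 says that patients are randomized by prepackaged envelope, "stratified based on the size and number of EMR performed during the procedure", and that "randomization will occur during the procedure immediately following resection". Both factors are therefore known before the arm is assigned. Section 5.7 says that randomization is "based on our current understanding of risk factors for post-resection scarring and stricture formation", and names defect size and number of resections. No cut-points, number of strata or blocking are given.

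**Analysis.** Section 7.2 gives the randomization subgroups one stated use: "Distributions across subgroups used in randomization will be compared to assess whether the randomization was successful in equalizing distributions of these prognostic variables" across the arms. For the primary hypothesis, "A student unpaired t-test will be performed to compare the incidence of successful lift in the area of prior EMR", with no stratum or covariate. Before the balance check it says "Baseline values for demographic, clinical, and outcome variables (primary and secondary) will be tabulated for the treatment groups" and "These analyses will help identify potential confounding variables to be used as covariates in sensitivity analyses". Those sensitivity analyses name no outcome, model or covariate.

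**Prognostic variables.** The list is open and has no time point in its own sentence. The variables "include variables such as presence of submucosal lift, esophageal caliber, need for esophageal dilation, and score on the Mayo Dysphagia Questionnaire".

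**The concern.** A trial that stratifies on factors it believes to be prognostic would normally use them in at least one analysis of the primary outcome. Here that depends on a choice made once the descriptive tables are available. With 20 patients, choosing covariates from the data leaves room for several different adjusted results, and a reader could not tell which was intended.

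Two things are at stake. The first is some power and precision, if size and number of EMR predict lift. The second is the credibility of any sensitivity analysis, since the study is meant to support larger ones (1.5.1).

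The prognostic list adds a smaller difficulty. Lift is an entry condition in 3.1, so it cannot vary at baseline, and at follow-up it is the primary endpoint. Need for dilation is described only after resection (3.1, 3.3, 6.3) and is a secondary endpoint. Neither has a described baseline value that could serve as a covariate.

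**Working it through.** **1. The plan's own figure.** Inputs from 7.1: lift 20% vs 80%, power 0.8, alpha 0.05 (taken as two-sided), 1:1.

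n per arm = [1.96·√(2·0.5·0.5) + 0.842·√(0.2·0.8 + 0.8·0.2)]² / 0.6² = (1.386 + 0.476)² / 0.36 = 9.6, so 10 per arm.

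The stated 20 patients reproduce. The calculation makes no use of strata. By exact enumeration at 10 per arm, power is 80.5% for the t-test on 0/1 data and 63.5% for Fisher's test.

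**2. Assumptions for the rest.** Two equally likely strata, with lift averaging 80% (ECM) and 20% (control) and differing between strata by a gap of 0, 20 or 30 points in both arms. None of these stratum rates is in the documents.

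**3. How much variance a stratum explains.** Lift variance within an arm is 0.8·0.2 = 0.16. A 20-point gap contributes 0.10² = 0.010 (6% of 0.16), and a 30-point gap 0.15² = 0.0225 (14%). An adjusted analysis can remove that share.

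**4. Power.** Simulation with N = 20, two-sided 0.05 and 20,000 trials per case (Monte Carlo SE about 0.3 points). *Adjusted* is a linear model of lift (0/1) on arm and stratum, which is the planned t-test with one term added.

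| Allocation | Gap | t-test (planned) | Adjusted | Stratified exact | Fisher |
|---|---|---|---|---|---|
| Blocks of 4 | 0 | 81% | 81% | 68% | 65% |
| Blocks of 4 | 20 | 82% | 84% | 72% | 66% |
| Blocks of 4 | 30 | 82–83% | 88% | 77% | 66% |
| Simple | 0 | 80% | 79% | 66–67% | 67% |
| Simple | 20 | 80% | 82% | 70% | 66–67% |
| Simple | 30 | 80% | 86% | 75% | 67% |

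**5. Type I error.** Take a null with lift 20%/80% by stratum in both arms. The t-test estimates a variance of 0.5·0.5 = 0.25, but with arms balanced within strata the relevant variance is 0.16. Its standard error is too large by √(0.25/0.16) = 1.25. With blocks of 4 its simulated error is about 1.4%, against about 4% adjusted. With simple allocation the unadjusted test stays at about 5%. There is no material inflation in either case.

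**6. Chance imbalance.** The shift in the crude difference is the gap times the between-arm difference in stratum share. Under simple allocation with 10 per arm, the SD of that difference is about √(0.25/10 + 0.25/10) = 0.224. This gives 0.20·0.224 = 4.5 and 0.30·0.224 = 6.7 points; simulation, which lets arm sizes vary, gives 4.6 and 6.9. With blocks of 4 the SDs are 1.3 and 2.0 points. For scale, the sampling SD of the crude difference is √(0.16/10 + 0.16/10) = 17.9 points. The blocked shift is therefore 1.3²/17.9² = 0.5% to 2.0²/17.9² = 1.2% of that variance, and the simple-allocation shift 7% to 15%.

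**7. More strata.** With four equal strata, no gap and simple allocation, the stratified exact test has about 60% power against 66% for Fisher's test, and 47% of trials have at least one stratum with only one arm. With blocks of 2 or 4 within strata it has 69–70% against 66–67%.

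**8. Dilation as a covariate.** Suppose 30% of non-lifting and 5% of lifting sites are dilated, and dilation depends on arm only through lift. Dilated shares are 0.8·0.05 + 0.2·0.30 = 10% (ECM) and 0.2·0.05 + 0.8·0.30 = 25% (control), average 17.5%. The lift difference is 0.04/0.10 − 0.01/0.25 = 0.36 among dilated patients and 0.76/0.90 − 0.19/0.75 = 0.591 among the rest. Weighted: 0.175·0.36 + 0.825·0.591 = 0.55, against 0.60 unadjusted. Assumed rates from 10%/2% to 50%/10% give 59 down to 52 points.

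**The case against.** The strongest reply is that 7.2 does foresee covariate sensitivity analyses, so a reader who infers that lift can never be examined by size or number of EMR goes too far. That stands: those factors could be chosen. What is missing is any commitment to choose them.

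Second, stratified allocation should already limit imbalance. This also stands if the envelopes are blocked within strata, since the shift is then small against sampling error. The larger shifts need allocation that is in effect simple. Section 5.2 states no blocking, but it does not state simple allocation either.

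Third, a reader might infer that the unadjusted test is invalid, or that a stratified exact test would beat the plan. Neither is supported. The t-test is conservative when arms are balanced within predictive strata and near nominal otherwise. The exact test gains only over Fisher's test, which the plan does not use, and has lower power than the planned t-test.

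Fourth, a reader might infer from the prognostic list that follow-up lift or dilation will be adjusted for. No sentence says so. The paragraph opens with baseline values and speaks of equalizing distributions, so baseline is the natural reading.

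Finally, this is a 20-patient feasibility trial, and adjustment choices can reasonably be simple. That argues for one two-level factor, not for leaving the choice open.

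**Conclusion.** The point holds as a modest gap in specification. No specified comparison of lift uses the stratification factors, and the sensitivity covariates are left to be picked after the tables are seen. Under the assumed rates with blocks of 4, adjustment is worth about 2 power points for a 20-point gap, about 6 for a 30-point gap and nothing for no gap. With simple allocation the pattern is similar, with a loss of about 1 point if the factors do not predict lift.

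All of this depends on size and number of EMR predicting lift. Section 5.7 links them to scarring and stricture, and 1.5.1 links failure to lift to inflammatory healing, but no document gives lift by stratum. The sample size and the unadjusted primary comparison are not called into question by this point. Harm from the prognostic list is possible but not shown.

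**What to change.** In 7.2:

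1. Pre-specify one analysis of lift adjusted for, or stratified by, a single two-level factor built from the size and number categories used to randomize. Fix its definition before any outcome is seen, and report it beside the unadjusted comparison. A linear model of lift on arm and that factor is the direct extension of the planned test. A stratified exact test is an alternative, with the lower power shown above.
2. Limit any other covariates to values obtained before randomization, and name them in advance. Remove lift and need for dilation from the list of prognostic variables. Baseline dysphagia score and pre-treatment esophageal diameter can stay.

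The cost is wording only, with no new data and no change in sample size. The downside is sparse strata: four should be avoided with 20 patients. If the envelopes use more than two categories, the merged factor will not match them exactly, and the plan should say so. It should also say whether the envelopes are blocked, because that decides how much chance imbalance remains.
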